10.2 SECONDARY EFFICACY PARAMETER(S)

The secondary efficacy parameter is the change from baseline to Week 8 in CGI-S score, which will be analyzed using the MMRM approach similar to the one used for the primary efficacy parameter. A sensitivity analysis will also be performed using the LOCF approach as described in Section 10.1.

To control the overall family-wise type I error rate for multiple comparisons across the primary and the secondary efficacy parameters, the fixed sequence testing procedure will be implemented, i.e., the efficacy analysis of the secondary efficacy parameter will be carried out inferentially only if the null hypothesis for the primary efficacy parameter is rejected.

| Term | Percentage |
|------------|------------|
| GMOs | ~10% |
| Organic | ~75% |
| Natural | ~70% |
| Artificial | ~15% |
| Organic | ~75% |
| Natural | ~70% |
| Artificial | ~15% |
| Organic | ~75% |
| Natural | ~70% |
| Artificial | ~15% |
| Organic | ~75% |
| Natural | ~70% |
| Artificial | ~15% |
| Organic | ~75% |
| Natural | ~70% |
| Artificial | ~15% |

11.0 SAFETY ANALYSES

The safety analysis will be performed for the double-blind treatment period and the down-taper period (only for safety parameters collected during the down-taper period), separately, using the Safety Population unless stated otherwise.

The safety parameters include adverse events (AEs), clinical laboratory parameters, vital signs, electrocardiographic (ECG) parameters, suicide risk assessment using the Columbia-Suicide Severity Rating Scale (C-SSRS), and the change from baseline in the age and gender adjusted height (evaluation of growth). For each safety parameter, the last nonmissing safety assessment before the first dose of double-blind investigational product will be used as baseline for all analyses of that safety parameter. Continuous variables will be summarized by number of patients and mean, SD, median, minimum, and maximum values. Categorical variables will be summarized by number and percentage of patients.

For patients who take the down-taper investigational product, the double-blind treatment period starts with the first dose of double-blind investigational product and ends with the last assessment date up to the first dose of the down-taper investigational product. The double-blind down-taper period starts one day after the end of the double-blind treatment period and ends with the last dose of the down-taper investigational product or the last visit, whichever is later.

For patients who do not take the double-blind down-taper investigational product, the double-blind treatment period starts with the first dose of double-blind investigational product and ends with the last dose of the double-blind investigational product or the last visit, whichever is later.

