#### **9.4.1                   Treatments Administered**

At Screening (Visit 1) and after consent/assent is obtained, patients will be given 3 placebo tablets and 1 placebo capsule to swallow to confirm their ability to swallow investigational product.

Investigational product in the form of tablets and capsules

Throughout the study, it is recommended that patients take the investigational product at the same time each day with food (Section 9.4.5).

Patients should participate in the double-blind down-taper period unless it is deemed not to be clinically appropriate by the Investigator.

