#### **9.7.6 Safety Analyses**

The safety analysis will be performed for the double-blind treatment period and double-blind down-taper period separately using the Safety Population. The safety parameters will include AEs, clinical laboratory parameters, vital sign measurements, ECG parameters, C-SSRS evaluations, and the change from baseline in the age and gender-adjusted height (evaluation of growth). For each safety parameter, the last assessment made before the first dose of double-blind investigational product will be used as the baseline for all analyses of that safety parameter.

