6.0 PATIENT POPULATIONS

Four populations will be considered in the statistical analysis of the study.

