6.3 SAFETY POPULATION

The Safety Population will consist of all patients in the Randomized Population who received at least 1 dose of double-blind investigational product.

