7.0 PATIENT DISPOSITION

The number of patients in 3 of the study populations (Randomized, Safety, and ITT) will be summarized by treatment group and study center; the Screened Population will be summarized overall only by study center.

Screen-failure patients (i.e., patients screened but not randomized) and the associated reasons for failure to randomize will be tabulated overall for the Screened Population. The number and percentage of patients who complete the double-blind treatment period and of patients who prematurely discontinue during the same period will be presented for each treatment group and pooled across treatment groups for the Safety Population. The number and percentage of patients who enter the down-taper period and of patients who complete the down-taper period will be presented for each treatment group and pooled across treatment groups for the Safety Population.

The reasons for premature discontinuation from the double-blind treatment period as recorded on the disposition pages of the electronic case report forms will be summarized (number and percentage) by treatment group for the Safety Population. Percentage of premature discontinuations will be compared overall and for each discontinuation reason between treatment groups using Fisher's exact test. All patients who prematurely discontinue during the double-blind treatment period will be listed by discontinuation reason for the Safety Population.

8.0

DEMOGRAPHICS AND OTHER BASELINE CHARACTERISTICS

Demographic parameters (age, sex, race, ethnicity) and other baseline characteristics (weight, height, body mass index) will be summarized descriptively by treatment group for the Safety and ITT populations, respectively. Baseline efficacy variables will be summarized by treatment group for the ITT Population.

Continuous variables will be summarized by number of patients and mean, SD, median, minimum, and maximum values. Categorical variables will be summarized by number and percentage of patients.

Comparability between treatment groups will be tested using a 2-way analysis-of-variance (ANOVA) model with treatment group and study center as the factors for continuous variables and a Cochran-Mantel-Haenszel (CMH) test, controlling for study center, for categorical variables.

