11.3 VITAL SIGNS

[figure not shown]
Descriptive statistics for vital signs (sitting radial pulse rate, sitting systolic and diastolic blood pressure, body weight and height) and their changes from baseline values at each visit, at the end of double-blind treatment period, and at the end of double-blind down-taper period will be presented by treatment group. Only patients with available baseline and at least 1 postbaseline assessment will be included in the summary.

[figure not shown]
Vital sign values will be considered PCS if they meet both the observed-value criteria and the change-from-baseline criteria listed in [Table 11.3–1](#). The number and percentage of patients with PCS postbaseline values will be tabulated by treatment group separately for the double-blind treatment period and the double-blind down-taper period. The percentages will be calculated relative to the number of patients with available baseline and at least 1 postbaseline assessment. The numerator will be the total number of patients with available baseline values and at least 1 PCS postbaseline value. A supportive listing of patients with PCS postbaseline values will be provided, including the PID number, and baseline and all postbaseline (including non-PCS) values.

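### Under the default rule, taper-period adverse event percentages are taken over the whole Safety Population, including patients who never took down-taper product and cannot have a taper-period event

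*SAP*

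**What the plan says.** **Analysis set.** SAP 11.0 analyses the down-taper period "only for safety parameters collected during the down-taper period), separately, using the Safety Population unless stated otherwise". Protocol 9.7.6 is to the same effect: "The safety analysis will be performed for the double-blind treatment period and double-blind down-taper period separately using the Safety Population".

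**Who is in it.** SAP 6.3 defines the Safety Population as "all patients in the Randomized Population who received at least 1 dose of double-blind investigational product". SAP 6.0 states that "Four populations will be considered in the statistical analysis of the study", and none of the four is limited to patients who entered the taper.

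**Entry is expected but not universal.** Protocol 9.4.1: "Patients should participate in the double-blind down-taper period unless it is deemed not to be clinically appropriate by the Investigator". Protocol 9.1.3, 9.3.3 and 9.4.5.3 also direct patients who stop early into the taper when that is clinically appropriate. SAP 7.0 reports "The number and percentage of patients who enter the down-taper period and of patients who complete the down-taper period" by treatment group.

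**Period boundaries.** SAP 11.0 defines a down-taper period only for patients who take down-taper product. For all others, the treatment period runs to the later of the last dose and the last visit.

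**Tables affected.** SAP 11.1 gives the number and percentage of patients with TEAEs separately for the two periods, and summarizes NEAEs for the taper. It names no denominator of its own for either. SAP 11.3 tabulates PCS vital signs separately by period and does name one: "The percentages will be calculated relative to the number of patients with available baseline and at least 1 postbaseline assessment".

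**The concern.** Under the SAP's own period rule, a patient who takes no down-taper product has no taper period in which to have an event. Counting that patient in the denominator of a taper-period percentage lowers the percentage without adding any information about stopping the drug.

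Protocol 9.2 says that the taper is there to make discontinuation symptoms less likely. The taper-period TEAE and NEAE tables are where such symptoms would appear, so their percentages are likely to be read as the risk among patients who tapered. Under the default rule they are something smaller. If entry differs between arms, they are smaller by different factors.

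**Working it through.** The documents state no taper-entry rate, taper event rate or taper denominator, so there is no figure in the plan to reproduce. The check is algebra, with assumed values labelled as such.

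**Inputs**
- Denominator under the default rule: all Safety Population patients in the arm, N (SAP 11.0, protocol 9.7.6).
- Entrants: E = e × N, where e is the entry fraction. Not given; assumed 70% to 95%.
- Events: only among entrants, at rate r (the period rule in SAP 11.0). Not given; assumed 10%, with 12% in one arm in the last example.
- N = 188 per arm for illustration, the re-estimated size for placebo and vilazodone in SAP 14.0.

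**Step 1: one arm**

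Reported percentage = (r × E) / N = r × e.

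At 75% entry: E = 0.75 × 188 = 141; expected patients with an event = 0.10 × 141 = 14.1. Over the Safety Population this is 14.1 / 188 = 7.5%; over entrants it is 14.1 / 141 = 10%.

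| Assumed entry | 10% among entrants is shown as |
|---|---|
| 95% | 9.5% |
| 90% | 9.0% |
| 83% | 8.3% |
| 75% | 7.5% |
| 70% | 7.0% |

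The 83% row would apply if everyone in the 17% dropout of SAP 14.0, and nobody else, skipped the taper. The documents do not say this.

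**Step 2: between arms**

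Reported ratio = (r_A / r_B) × (e_A / e_B).

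- Equal entry: e_A / e_B = 1. The ratio is unchanged and only the absolute percentages fall.
- Assumed entry 75% against 90%: 0.75 / 0.90 = 0.83. A rate of 10% among entrants in both arms is shown as 7.5% against 9.0%. Rates of 12% against 10% are shown as 0.12 × 0.75 = 9.0% against 0.10 × 0.90 = 9.0%, so a ratio of 1.20 becomes 1.00.
- Assumed entry 70% against 95%: 0.70 / 0.95 = 0.74.

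**Step 3: vital signs**

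SAP 11.3 departs from the default, so Step 1 does not carry over directly. Its denominator asks for a baseline and a postbaseline assessment, without saying in which period the latter must fall. There are two readings:
- Within-period: only patients with an assessment in the taper count, and there is no dilution.
- Any postbaseline value: a patient who took no taper product but has a treatment-period value counts in the denominator and cannot enter the taper numerator. This includes a patient whose Week 9 visit (which protocol 9.1.3 requires of all randomized patients) falls in the treatment period under SAP 11.0.

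The text does not settle which is meant.

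**The case against.** **The AE denominator is inferred.** SAP 11.0 names an analysis set, SAP 11.1 writes out no denominator, and the default allows exceptions. SAP 4.0 places the table specifications in a separate document, and some safety text is redacted. A taper denominator may therefore exist elsewhere. This limits certainty about what will be programmed. It does not change what follows from the rule in the SAP.

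**Not every taper-period rate is affected.** A reader might infer that all taper tables are diluted. The documents do not support this: vital-sign PCS percentages have their own denominator, and continuous vital-sign summaries are restricted to patients with baseline and postbaseline data.

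**The 17% is not a non-entry rate.** A reader might take it as one. It is planned dropout, and the protocol directs early discontinuers into the taper when clinically appropriate. Some completers, on the other hand, may not taper.

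**No direction between arms is established.** A reader might infer that the less tolerated drug will look safer to stop. That requires more non-entry in that arm, and nothing in the documents shows it.

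**Entrants are a selected group.** Taper entry follows randomization, so restricting to entrants does not give a randomized comparison. Incidence among all treated patients is also a coherent quantity. Both statements are correct. Even so, a percentage labelled as taper-period is more useful when it describes patients who had a taper period.

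**The effect is contained.** Safety is descriptive, no visible text tests taper AE rates, and SAP 7.0 reports entry by arm, so a reader could rescale the percentages. Discontinuation symptoms are not named in the objectives. This limits the importance of the point, but it leaves the correction to the reader, table by table.

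**Conclusion.** The point holds for taper-period TEAE and NEAE percentages. Under the stated default, each equals the rate among entrants times the entry fraction, so it understates the rate in patients who tapered whenever entry is incomplete. For a 10% rate among entrants, the shown figure is 7.0% to 9.5% over an assumed 70% to 95% entry.

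The between-arm ratio is distorted only if entry differs by arm. The factors of 0.83 and 0.74 rest entirely on assumed unequal entry, and neither the existence nor the direction of a difference can be read from the documents.

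For PCS vital signs the finding is narrower: the denominator is loosely worded for the taper and may or may not include patients without a taper assessment.

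Efficacy conclusions are untouched. The SAP should be corrected because the rule as written gives a less informative percentage and the at-risk denominator is simple to state.

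**What to change.** - **SAP 11.0 and 11.1:** state that taper-period TEAE and NEAE percentages use Safety Population patients who took at least one dose of down-taper product. SAP 11.0 already identifies this group when it sets the period boundaries.
- **SAP 11.3:** state that taper-period PCS percentages use patients in that group who have a baseline and at least one assessment within the taper period.
- **Reading the tables:** present them with the entry counts by arm from SAP 7.0, and note that entrants are a post-randomization subset, so comparisons between arms stay descriptive.
- If the separate table specifications already use these denominators, the SAP need only say so.

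The cost is one paragraph and a denominator flag in the table programs. No new data are needed. Taper-period percentages will look slightly higher than under the present rule.

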11.1 ADVERSE EVENTS

Adverse events will be coded by system organ class and preferred term using the *Medical Dictionary for Regulatory Activities*, version 17.0 or newer.

An AE (classified by preferred term) that occurs during the double-blind treatment period or during the down-taper period will be considered a treatment-emergent adverse event (TEAE) if it was not present before the date of the first dose of double-blind investigational product, or was present before the date of the first dose of double-blind investigational product and increased in severity during the double-blind treatment period or during the down-taper period, respectively. If more than 1 AE was reported before the date of the first dose of double-blind investigational product and coded to the same preferred term, the AE with the greatest severity will be used as the benchmark for comparison with the AEs occurring during the double-blind treatment period or during the down-taper period that were also coded to that preferred term. An AE that occurs more than 30 days after the date of the last dose of double-blind investigational product in the study will not be counted as a TEAE but will be included in the listings.

An AE occurring during the down-taper period will be considered a newly emergent AE (NEAE) if it is not present before the start of the down-taper period or was present before the start of the down-taper period but increased in severity during the down-taper period. The NEAEs during the down-taper period will be summarized by body system, preferred term, and treatment group.

The number and percentage of patients reporting TEAEs in each treatment group will be tabulated by system organ class and preferred term and further categorized by severity and causal relationship to the investigational product, for both the double-blind treatment period and the double-blind down-taper period, separately. If more than 1 AE is coded to the same preferred term for the same patient, the patient will be counted only once for that preferred term using the greatest severity and strictest causality for the summarization by severity and by causal relationship to the investigational product, respectively.

The distribution of TEAEs by severity and causal relationship to the investigational product will be summarized by treatment group separately for the double-blind treatment period and the double-blind down-taper period, separately.

A common TEAE during the double-blind treatment period will be summarized in 2 ways: $\geq 1\%$ of patients in any treatment group and $\geq 2\%$ of patients in any treatment group. The incidence of common TEAEs will be summarized separately by preferred term and treatment group and will be sorted by decreasing frequency for the vilazodone treatment group.

A serious adverse event (SAE) that occurred on the date of the first dose of double-blind investigational product and up to 30 days after the date of the last dose of double-blind investigational product, inclusive, will be considered an on-therapy SAE. The number and percentage of patients who have on-therapy SAEs will be summarized by preferred term and treatment group and will be sorted by decreasing frequency for the vilazodone treatment group. In addition, the incidence of on-therapy SAEs that led to death will be summarized separately by treatment group and preferred term.

The number and percentage of patients in the Safety Population who have AEs leading to premature discontinuation of the investigational product will be summarized by preferred term and treatment group and will be sorted by decreasing frequency for the vilazodone treatment group.

Listings will be presented for patients with SAEs, patients with AEs leading to discontinuation, and patients who die (if any) for the Screened Population. All patients with SAEs, including those reported during the screening period or more than 30 days after the date of the last dose of the double-blind investigational product, and patients discontinuing because of AEs before taking double-blind investigational product will be included in these listings.

[figure not shown]
11.2 CLINICAL LABORATORY PARAMETERS

Descriptive statistics for clinical laboratory values (in SI units) and changes from the baseline values at each assessment time point (including the end of the double-blind treatment period) will be presented by treatment group for the following laboratory parameters:

[REDACTED]

[REDACTED]

[figure not shown]

A horizontal bar chart consisting of 10 bars of varying lengths. Each bar is preceded by a small black square marker. The bars are arranged from top to bottom in the following order of lengths: very long, long, very long, long, medium, short, short, medium, long, very long.

11.3 VITAL SIGNS

[figure not shown]
Descriptive statistics for vital signs (sitting radial pulse rate, sitting systolic and diastolic blood pressure, body weight and height) and their changes from baseline values at each visit, at the end of double-blind treatment period, and at the end of double-blind down-taper period will be presented by treatment group. Only patients with available baseline and at least 1 postbaseline assessment will be included in the summary.

[figure not shown]
Vital sign values will be considered PCS if they meet both the observed-value criteria and the change-from-baseline criteria listed in [Table 11.3–1](#). The number and percentage of patients with PCS postbaseline values will be tabulated by treatment group separately for the double-blind treatment period and the double-blind down-taper period. The percentages will be calculated relative to the number of patients with available baseline and at least 1 postbaseline assessment. The numerator will be the total number of patients with available baseline values and at least 1 PCS postbaseline value. A supportive listing of patients with PCS postbaseline values will be provided, including the PID number, and baseline and all postbaseline (including non-PCS) values.

11.4 ELECTROCARDIOGRAM

Descriptive statistics for ECG parameters (heart rate, PR interval, QRS interval, RR interval, QT interval, and QTc interval) at baseline and changes from baseline values at each assessment time point (including the end of the double-blind treatment period) will be presented by treatment group. The QTc will be calculated using both the Bazett and Fridericia corrections. Only patients with available baseline and at least 1 postbaseline assessment will be included in the summary.

12.0 **HEALTH OUTCOMES ANALYSES**

Not applicable.

13.0 BLINDED INTERIM ANALYSIS

A blinded interim analysis will be conducted when approximately 75% of randomized patients have either completed the study or discontinued from the study. The blinded interim analysis is to obtain an estimate of the pooled standard deviation of the change from baseline to Week 8 in the CDRS-R total score. If the estimated pooled standard deviation is larger than the assumed pooled standard deviation specified in Determination of Sample Size (Section 14.0), the sample size may be increased to ensure an adequate power. However, due to the difficulties in recruiting pediatric patients with MDD, the total number of patients of the study will be capped at 500 (200 per treatment group for placebo and vilazodone, 100 for the fluoxetine treatment group). Detailed specification of the blinded interim analysis will be provided in the blinded interim analysis plan, a separate document. The interim analysis of sample size re-estimation will be performed by an independent statistician.

